## **9 Participant Recruitment**

All Aboriginal patients admitted to participating hospital sites who meet the study criteria (Section 7.2) will be approached to participate by the investigator. If the person agrees for their name to be given to the clinical trial team, a team member will preferably see the person in hospital within two days of referral in order to further discuss the project and obtain written informed consent. If, however, the person is discharged before the baseline assessor is able to attend in order to gain consent and complete an assessment or the baseline assessor cannot attend the hospital in person due to hospital or patient-related restrictions, the assessor will telephone them, to see if they would be interested in hearing more about the project/being involved. If the person agrees, the assessor will then see the person at their home, mutually agreed location or will contact via telephone/telehealth facility in order to further discuss the project, obtain consent, and complete the baseline assessment. Project information will be given to the patient in hard copy, digitally or verbally based upon whether it is safe and feasible for a baseline assessor to visit the patient in person and the patient’s access to electronic and digital communication platforms including email and telehealth programs. Patients will give their consent to participate either in wet-ink writing; via

electronic or digital signature or verbally. In the latter scenario the baseline assessor will read aloud information from the Participant Information and Consent Form to provide the patient with project information. The patient's verbal decision will be recorded in the CRF at the recruiting hospital. The patient will then be sent a copy of the study's information sheet. In the case of the investigator not having had the opportunity to approach the person whilst in hospital, the investigator will telephone them, to see if they would be interested in hearing more about the project/being involved. If the person agrees for their name to be given to the clinical trial team, the baseline assessor will then see the person at their home, mutually agreed location or will contact via telephone/telehealth facility in order to further discuss the project, obtain informed consent, and complete the baseline assessment and processes will proceed as above. The informed consent process will involve the use of 'aphasia friendly' information to accommodate patients with communication disorders, those with other cognitive issues typically associated with brain injury, and those with limited literacy skills. The process will also involve a relevant interpreter as needed. In the case of patients with a decision making disability who are incapable of providing consent, we will apply a Research Decision Maker consent pathway. Within this study, exclusion on the basis of inability to give consent would discriminate against individuals with severe brain injury, as the intervention provides additional client and family support and monitoring, rather than being a specific activity based or pharmaceutical intervention.

Participants can be recruited to the study at any time within six weeks post injury.

## **10 Study Assessment and Procedures**

In this study, 'baseline' refers to both individual participant status and the status of services provided at each site during the Control period i.e. before the intervention period commences. As part of the stepped-wedge project design, the length of service baseline (i.e. usual care control period, where intervention has not been introduced) will vary across sites depending on when they are randomised to receive the intervention. Those sites receiving the intervention in 2018 will have shorter control periods than those not receiving interventions until 2019.

### **10.1 Screening**

All Aboriginal stroke and traumatic brain injury patients over the age of 18 admitted to hospital will be screened for inclusion in the study as per the eligibility criteria outlined in section 7.2. Those screened by the investigator and deemed not eligible for the study will be entered into a screening log, which outlines the reason for non-inclusion in the study.

### **10.2 Participant Assessment Schedule**

#### **10.2.1 Baseline Assessments**

Assessors trained in the use of all assessment tools will collect all patient related data. Required study assessments are outlined in Appendix 1 – Schedule of Assessments.

Individual baseline data will preferably be collected on the same day as consent (or within 2 days if recruited over a weekend) from participants who meet all inclusion criteria and have provided consent. The assessment will be completed within 42 days of injury. The assessments completed at baseline will be: modified Rankin Score (mRS), Functional Independence Measure (FIMTM), Hospital Anxiety Depression Scale.

Baseline data collection will include the collection and documentation of:

- 1) Demographic details including age, gender, languages spoken, language group, residence location (metro/rural/remote), premorbid employment, Aboriginal or Torres Strait Islander status, living arrangements at the time of admission
- 2) Details related to brain injury type (stroke vs traumatic brain injury), and pathological sub-types of each (stroke: ischaemic vs haemorrhagic; TBI: closed, penetrating, blast, crush - as per IMPACT core data set), hemisphere(s) involved, first or recurrent/subsequent injury, and severity as determined by the National Institutes of Health Stroke Scale (for the post stroke participants) and the Glasgow Coma Scale (for the post traumatic brain injury participants). Cause of the TBI i.e. road traffic incident vs violence will also be recorded.
- 3) Past medical history, brain injury history and comorbidities.
- 4) The assessment tasks should be completed in a single session. If the participant is unable to complete assessment tasks in a single session, they must be completed on the same day if possible (i.e. over a morning and afternoon session). If this is not possible, the assessments should take place on consecutive days. Protocol deviations will be recorded if assessment sessions are not completed on the same day or if sessions are completed later than the due date +/- 7 days.

### **10.2.2 Week 12 (84 days post injury +/- 14 days) follow up visit**

The participants will be followed up at their place of residence, in the hospital or Aboriginal Medical Service clinic as convenient for the participant, or by phone/telehealth facilities as appropriate by a blinded assessor. The assessment tasks should be completed in a single session. If the participant is unable to complete assessment tasks in a single session, they must be completed on the same day if possible (i.e. over a morning and afternoon session). If this is not possible, the assessments should take place on consecutive days. Protocol deviations will be recorded if assessment sessions are not completed on the same day or if sessions are completed later than the due date +/- 14 days.

During this visit, the modified Rankin Score (mRS), Functional Independence Measure (FIMTM), Modified Caregiver Strain Index and Hospital Anxiety and Depression Scale will be re-administered, as well as the EuroQol-5D-3L. See Appendix 1 for details.

At this visit the participant and/or their carer will be asked about their general health to determine if there have been any adverse events since their last visit.

As part of the economic analysis and as part of general service data (see Section 10.4 below), data will be collected for all patients at this visit regarding inpatient and outpatient rehabilitation related sessions (rehabilitation specialist, allied

health sessions). In addition, hospital length of stay, cost of transfer from rural to metro sites, private services used up to 12 weeks post onset (rehabilitation services, allied health sessions), cost of travel associated with patient accessing services, rehabilitation costs of medical/allied health specialists visiting patients in their homes/remote communities, number of associated services required e.g., respite care, cost of current Aboriginal Liaison Officer services, specialist ABIC services, cost of interpreter services. Also costed will be carers' and brain injury survivors' loss of income or household productivity impacts. A record of pre-event (stroke or ABI) services use will also be captured to account for service use that is only applicable to the current condition.

As part of the process evaluation, a brief questionnaire will be completed with the assistance of the assessor, focusing on hospital experiences and brain injury related services to date. Another questionnaire surrounding the services of the ABIC as relevant to the intervention period will also be administered. However in order to maintain blinding of the main assessor, another independent assessor will administer this questionnaire

### **10.2.3 Week 26 (182 days – 14 days / + 28 days follow up visit**

The participants will be followed up at their place of residence, in the hospital or Aboriginal Medical Service clinic as convenient for the participant, or by phone/telehealth facilities as appropriate by a blinded assessor. The assessment tasks should be completed in a single session. If the participant is unable to complete assessment tasks in a single session, they must be completed on the same day if possible (i.e. over a morning and afternoon session). If this is not possible, the assessments should take place on consecutive days. Protocol deviations will be recorded if assessment sessions are not completed on the same day or if sessions are completed later than the due date – 14 days / +28 days.

During this visit, the modified Rankin Score (mRS), Functional Independence Measure (FIMTM), Modified Caregiver Strain Index and Hospital Anxiety and Depression Scale will be re-administered, as well as the EuroQol-5D-3L.

At this visit the participant and or their carer will be asked about their general health to determine if there have been any adverse events since their last visit.

As part of the economic analysis and as part of general service data (see Section 10.4 below), data will be collected as per the 12 week visit for all patients at this visit regarding inpatient and outpatient rehabilitation related sessions (rehabilitation specialist, allied health sessions) occurring between the 12-26 week period (see previous Section 10.2.2).

As part of the process evaluation, a brief questionnaire will be completed with the assistance of the assessor, focusing on hospital experiences and brain injury related services to date. Another questionnaire surrounding the services of the ABIC as relevant to the intervention period will also be administered. However in order to maintain blinding of the main assessor, another independent assessor will administer this questionnaire. Individual interviews with a sub-section of participants (n=10) exploring participants' satisfaction with the Aboriginal Brain Injury Coordinator service will be conducted at 26 weeks

### 10.3 Assessment details

#### 10.3.1 The Euro QOL-5D-3L

The Euro QOL-5D-3L developed by the Euroqol group, has two sections: the EQ-5D descriptive system which measures the health-related dimensions of mobility, self-care, usual activities, pain/discomfort, and anxiety/depression on a 3 point scale, and the EQ visual analogue scale (EQ VAS) – a vertical where the endpoints are labelled ‘Best imaginable health state’ and ‘Worst imaginable health state’. It has been used with stroke and traumatic brain injury survivors, validated in many different countries and cultural settings, and can be administered by face to face or telephone interview, or as a self-or proxy mail out.

The Euro QOL-5D-3L will be completed at 12 and 26 weeks post injury.

#### 10.3.2 Modified Rankin Scale

The mRS is a scale commonly used for measuring the degree of disability or dependence in the daily activities of individuals post-stroke. The mRS has an administration time of approximately 5 minutes. The scale contains 7 points from 0-6, ranging from perfect health without symptoms to death.

The mRS will be administered at baseline and at 12 and 26 weeks post injury. It is validated for administration by telephone as well as face to face. All assessors will hold formal training certificates in the use of this tool.

#### 10.3.3 Functional Independence MeasureTM27

The FIMTM is a basic indicator of level of disability, and measures changes in a patient’s functional abilities. It consists of 18 items, grouped into 2 subscales - motor (13 items) and cognition (5 items). Each item is scored on a 7 point scale, which ranges from 1-7. On the scale, 1 represents total dependence in a particular functional skill and 7 represents complete independence.

The total score for the FIM motor subscale (the sum of the individual motor subscale items) ranges from 13 to 91.

The total score for the FIM cognition subscale (the sum of the individual cognition subscale items) ranges from 5 to 35.

The total score for the FIM instrument (the sum of the motor and cognition subscale scores) will be a value between 18 and 126.

The FIMTM will be administered at baseline and at 12 and 26 weeks post injury. It is validated for administration by telephone as well as face to face interview, and by proxy.

All assessors will hold formal training certificates in the use of this tool.

#### 10.3.4 Modified Caregiver Strain Index

The Modified Caregiver Strain Index is a 13-item questionnaire administered to carers and concerns burden of care-giving. Carers are required to respond with ‘yes, on a regular basis’ (=2 points), ‘yes, sometimes’ (=1 point) or ‘no’ (=0 points). Test instructions indicate that any positive answer may indicate a need for intervention in that area. A total score of 7 or higher indicates a high level of stress.

The Modified Caregiver Strain Index will be administered at 12 and 26 weeks post injury.

### **10.3.5 Hospital Anxiety and Depression Scale**

The Hospital Anxiety and Depression Scale is a 14 item questionnaire designed to measure anxiety and depression in a general medical population and takes between 2-5 minutes to complete. There are seven items for anxiety and seven for depression and the two areas are scored separately. There is a 4 point scale for each. For both areas, scores that are less than 7 are considered ‘non-cases.’ Scores between 8-10 are considered mild, 11-14 = moderate, and 15-21 = severe.

The Hospital Anxiety and Depression Scale will be administered at baseline, 12 and 26 weeks post injury.

## **10.4 Service data**

Site data will be collected with respect to services delivered to each participant for six months during the control and intervention periods. This data will consist of:

- Occasions of service per allied health discipline (Physiotherapy, Occupational Therapy, Speech Pathology, Social Work, Dietetics; Clinical Psychology/ Neuropsychology; Prosthetics/Orthotics; Therapy Assistant; inpatient and outpatient)

The data will be collected through a medical file review process and through access to hospital administrative data systems as needed.

In addition, *Minimum Process of Care Indicators* will capture data on whether key processes of care occurred while the patient was in hospital and/or within 26 weeks of injury.

The data collection will:

- involve extraction of relevant data from medical file (audit process)
- be undertaken by an independent blinded auditor
- include hospital sites at which patients were admitted for the index admission and any related contiguous admission or related admission
- will include inpatient and hospital notes
- be audited cumulatively i.e. they will be checked for occurrence across the 26 week follow up period
- note the timing of items with reference to the index admission will be recorded
- occur at 6 month intervals

The Minimum Processes of Care are the following:

- patient assessed by allied health within 48 hours of admission
- Aboriginal Liaison Officer involved during inpatient stay
- language noted in medical file
- interpreter used if Aboriginal language is participant’s primary language
- telephone or face to face contact with family made by any allied health staff during inpatient stay
- Aboriginal brain injury educational resource provided during inpatient stay
- inpatient allied health service provided (any discipline)
- discharge plan developed with patient and family at family conference

- outpatient allied health service provided (any discipline)

In the case of participants returning from a metropolitan hospital to a regional/rural/remote location:

- verbal contact made by the metropolitan hospital with local rural service provider (hospital and local Aboriginal Medical Service)
- discharge report from metropolitan hospital sent to rural service provider (hospital and local Aboriginal Medical Service)

### **10.5 Resource utilisation and valuation of costs**

A standardised protocol ensuring uniform data collection will be used to calculate resource use in participants during the control and intervention phases of this study. Details of all services used will be collected, by the blinded assessor, for all participants until 26 weeks post injury.

As noted above, the following data will be collected for all patients: hospital length of stay, ambulance transfers, emergency hospital visits, inpatient and outpatient rehabilitation related sessions (rehabilitation specialist, allied health sessions), general practice services, bush medicine services, therapy aids and equipment and any informal care by family or friends. In addition, for the purposes of this analysis specifically, cost of transfer from rural to metro sites, private services used up to 26 weeks post brain injury (rehabilitation services, allied health sessions), cost of travel associated with patient accessing services, rehabilitation costs of medical/allied health specialists visiting patients in their homes/remote communities, number of associated services required e.g., respite care, cost of current Aboriginal Liaison Officer services, specialist ABIC services, cost of interpreter services. Also costed will be carers' and brain injury survivors' loss of income or household productivity impacts. A record of pre-event (stroke or ABI) services use will also be captured to account for service use that is primarily applicable to the current condition.

Two methods will be used to collect resource use information. First, as noted above, the eCRF will capture brain injury related therapy activity including amount and discipline of therapy received. Second, a participant interview will capture changes to employment and services utilised as a result of the brain injury including: length of acute hospital stay; discharge destination; inpatient and outpatient rehabilitation; hospital readmissions; GP visits; community and health care service use; medication use (including medication prescribed after the stroke for anxiety and depression); allied health therapies; respite and informal care services; and changes to participant and carer employment; and any aids/devices provided. The additional costs of providing the interventions (program-related costs) will also be estimated as part of the Economic Evaluation.

Resource utilisation information will be used to estimate the cost effectiveness of both the cultural training and the implementation of the ABIC (see section 12.5). In brief, cost description analyses of each comparator group to 26 weeks will be detailed. Cost items will be valued for the reference year 2020. Where prices in 2020 are unavailable, adjustment to the real price will be made using the published health sector specific deflator/inflators. Incremental cost-effectiveness ratios or the net difference in costs and outcomes will be calculated for the intervention group relative to the control group. Sensitivity and uncertainty (probabilistic multivariable [Monte-Carlo simulated])

analyses to account for variability in point estimates will be performed to assess the robustness of results.

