
Study Hypotheses:
	
Primary hypothesis
 
H1. Compared to usual care, implementation of the proposed intervention package (IP) will result in an at least 15 point higher score on the Euro QOL–5D-3L VAS at 26 weeks post injury
 
Secondary hypotheses:
 
H2a. Compared to usual care, implementation of the IP will result in significant improvement in service delivery at 12 and 26 weeks post injury as related to increased occasions of service
 
H2b. Compared to usual care, implementation of the IP will result in significant improvement in service delivery at 12 and 26 weeks post injury as related to increased compliance with minimum process of care indicators
 
H3. Compared to usual care, implementation of the IP will result in significant improvement in neurological disability (Modified Rankin Scale) and independence (Functional Independence Measure) at 12 and 26 weeks post injury
 
H4. Compared to usual care, implementation of the IP will result in significantly reduced carer burden (Modified Caregiver Strain Index) and less brain injury survivor anxiety and depression (Hospital Anxiety and Depression Scale) at 12 and 26 weeks post injury.
 
H5. The culturally sensitive IP will be more cost-effective (additional benefits gained will justify additional costs for delivering the intervention; may lead to potential cost-offsets from less severe disease) than usual care at 12 and 26 weeks post injury
 
H6. The IP will be acceptable to health professionals and Aboriginal participants and their families, and the role

	of the Aboriginal Brain Injury Coordinator a feasible one
Primary Outcome measure	Blinded assessment of the Euro QOL–5D-3L VAS score at 26 weeks post brain injury.

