### 13.6.2 Assessment of Causality

The blinded assessor is obligated to assess the relationship between study treatment and the occurrence of each AE/SAE. The blinded assessor will use clinical judgment to determine the relationship. Alternative causes, such as natural history of the underlying diseases, concomitant therapy, other risk factors, and the temporal relationship of the event to the treatment period will be considered.

The causal relationship to the study treatment assessed by the blinded assessor should be assessed using the following classifications:

- Not Related** In the Assessors opinion, there is not a causal relationship between the study product and the adverse event.
- Unlikely** The temporal association between the adverse event and study treatment is such that the study treatment is not likely to have any reasonable association with the adverse event.
- Possible** The adverse event could have been caused by the study treatment.
- Probable** The adverse event follows a reasonable temporal sequence from the time of study treatment, abates upon discontinuation of treatment and cannot be reasonably explained by the known characteristics of the study participant’s clinical state.
- Definitely** The adverse event follows a reasonable temporal sequence from the time of study treatment start or reappears when study treatment is reintroduced.

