### *3. Blinding*

All assessors will be independent of the researchers involved in the intervention or the trial. However, assessors in rural areas will most likely be aware of whether their local hospital is in intervention or control phase. Therefore it is not possible to blind the assessors, patients or most investigators on whether the patients received intervention or not. However, follow-up assessors will be blinded to the baseline assessment of any given participant. All analyses will be carried out by a statistician who is blinded to the randomization of sites and allocation of individual patients to intervention or control. Assessor blinding will be examined according to CONSORT guidelines at 12 weeks. The James blinding index will be used to assess the effectiveness of the blinding.

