### Anxiety/Depression

- I am not anxious or depressed
- I am moderately anxious or depressed
- I am extremely anxious or depressed

To help people say how good or bad a health state is, we have drawn a scale (rather like a thermometer) on which the best state you can imagine is marked 100 and the worst state you can imagine is marked 0.

We would like you to indicate on this scale how good or bad your own health is today, in your opinion. Please do this by drawing a line from the box below to whichever point on the scale indicates how good or bad your health state is today.

**Your own  
health state  
today**

Best  
imaginable  
health state

100

90

80

70

60

50

40

30

20

10

0

Worst  
imaginable  
health state

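### The blinded assessor who administers the week-26 VAS is also given coordinator-service data that can reveal the condition, the protocol's blinding statements conflict, and blinding is checked only at week 12

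*Protocol*

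**What the plan says.** **The blinding claim.** The synopsis gives the primary outcome as "Blinded assessment of the Euro QOL–5D-3L VAS score at 26 weeks post brain injury". Sections 10.2.2 and 10.2.3 assign the week-12 and week-26 visits to a blinded assessor. In Appendix 1 the EuroQol, mRS, FIM, resource utilisation, adverse events and SAEs at both visits all carry the code for that one role.

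**Service data.** Section 10.5 says: "Details of all services used will be collected, by the blinded assessor, for all participants until 26 weeks post injury". Its list of items includes "cost of current Aboriginal Liaison Officer services, specialist ABIC services, cost of interpreter services". Section 10.2.2 has the same ABIC item among the week-12 visit data, and 10.2.3 collects data on the same basis at week 26.

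**The safeguard.** For the questionnaire about the ABIC, 10.2.2 provides that "in order to maintain blinding of the main assessor, another independent assessor will administer this questionnaire". Section 10.2.3 repeats this for week 26.

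**The concession.** The Blinding paragraph of 16.4.2 notes that rural assessors will probably know their local hospital's phase and concludes: "Therefore it is not possible to blind the assessors, patients or most investigators on whether the patients received intervention or not". It then says that follow-up assessors are blinded to the participant's baseline assessment, and plans a James index. The only stated time for examining assessor blinding is 12 weeks.

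**Relatedness.** Section 13.6.2 says: "The blinded assessor is obligated to assess the relationship between study treatment and the occurrence of each AE/SAE". Section 13.5 requires this rating with the initial SAE report.

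**The concern.** A record of ABIC contact identifies an intervention-period participant. If the person who administers the VAS also records that contact, the form supplies the information that the separate-assessor rule was written to withhold.

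The VAS is subjective and under 10.3.1 may be given by face-to-face or telephone interview or completed by proxy, so an assessor who knows the condition has some room to influence it. The mRS and FIM, scored by the same role, are at least as exposed. A report could also claim a blinded primary outcome that 16.4.2 says is not achievable, supported by a check made 14 weeks (26 − 12) before the outcome is measured.

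**Working it through.** **Can the service data reveal the condition?**
1. Appendix 1: one role, the blinded assessor, has both EuroQol and resource utilisation at weeks 12 and 26.
2. Sections 10.2.2 and 10.5: the data on service use include ABIC services.
3. Section 11.1.2: a participant recruited at a site without an ABIC service receives none, even after transfer to a region that has one. ABIC contact therefore implies the intervention condition.
4. Sections 10.2.2 and 10.2.3: the ABIC questionnaire goes to someone else to protect the blind. Steps 1 to 3 allow the same information in by another form.

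**What is the assessor blinded to?** The synopsis, 10.2.2, 10.2.3 and Appendix 1 use the word blinded without qualification. Section 16.4.2 says blinding to condition is not possible and leaves only blinding to the baseline assessment. Both statements cannot describe the same outcome.

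**When is blinding tested?** The primary outcome is at week 26; the check is at week 12. Service and adverse-event questions are asked at week 12 and again at week 26, so unblinding that happens after week 12 goes unobserved.

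**Relatedness.** The criteria in 13.6.2 refer to the timing of the event relative to treatment and, for a probable rating, to improvement once treatment stops. A masked rater may lack those facts. Under 13.1 and 13.3 the rating also decides whether a non-serious event is recorded at all.

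**Illustration of size.** The protocol gives no figure for assessor bias. Its only design calculation is in 16.3: 15 points, SD 25, 80% power, 5% significance, 90 participants before adjustment for the design.
- Reproducing the 90: 2 × (1.960 + 0.842)² × 25² / 15² = 43.6 per arm by the normal approximation. The two-sided t-test version gives 44.6, so 45 per arm and 90 in total. The 5% level is therefore two-sided.
- Standard error implied by the stated power: 15 / (1.960 + 0.842) = 15 / 2.80 = 5.35 points.
- With no true effect and a bias b, type I error = 1 − Φ(1.96 − b/5.35) + Φ(−1.96 − b/5.35).

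| Assumed bias b (VAS points) | b as share of 15 points | Type I error |
|---|---|---|
| 1 | 7% | 5.4% |
| 3 | 20% | 0.0808 + 0.0059 = 8.7% |
| 5 | 33% | 0.1524 + 0.0019 = 15.4% |

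The values of b are assumptions. The calculation takes the stated power at face value and supposes that all assessors shift scores in the same direction.

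**The case against.** **The assignment is not explicit.** Section 10.5 names two collection methods, the eCRF and a participant interview, and its interview list does not mention the ABIC. The ABIC item stands in a passive list with no collector named, ABIC activity is already logged in the e-CRF (11.2.2), and programme costs are estimated separately. This stands in part: a reader can construct a consistent arrangement. But the sentence on all services used, the visit data in 10.2.2 and the coding in Appendix 1 assign the item to the assessor as written.

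**Much of the blind is already conceded.** Section 16.4.2 admits that assessors cannot be blinded, and the VAS is the participant's own rating: "We would like you to indicate on this scale how good or bad your own health is today, in your opinion". Participants know what they received, so assessor knowledge is a secondary route to bias. This stands. A reader might infer that the form alone destroys an otherwise intact blind; the documents do not support that. They do not fix the order of questions within a visit, and do not say whether one person does both visits.

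**Masked relatedness rating is possible.** A reader might infer that a blinded assessor cannot rate relatedness, or that such a rating is worthless for safety. Neither follows. Masked rating is routine in blinded trials; the gap is only between the criteria in 13.6.2 and what a masked rater would know. Handing the rating to site investigators would be worse: most of them cannot be blinded (16.4.2), and they would then control which non-serious events are recorded in each condition.

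**An early blinding check is defensible.** Late guesses may reflect the outcome observed. That is a reason to keep week 12, not to omit week 26.

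**Conclusion.** The point holds as a defect in data-collection roles and in the blinding claim. As written, the protocol lets the assessor of the primary outcome receive information that identifies the condition, against its own safeguard. It describes the primary outcome as blinded in some places and says blinding is not possible in another. It has no blinding check at the time of the primary outcome.

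The size of any bias is unknown. The rise to 8.7% to 15.4% shows only what an assumed shift of 3 to 5 points would do. It should not be read as an estimate of the trial's false-positive rate, because the documents give no bias figure and the self-rating by unblinded participants is a separate matter that assessor blinding cannot cure. How much the service questions add to the unblinding already conceded also cannot be determined from the documents.

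**What to change.** 1. Take ABIC contacts and costs only from the ABIC e-CRF log (11.2.2), and remove the item from the assessor's data in 10.2.2, 10.2.3 and 10.5.
2. At each follow-up visit, require the VAS first, then the other outcome scales, and only then the service-use and adverse-event questions.
3. Keep the week-12 blinding check and add the James index at week 26, straight after the VAS. Report it with the caution that late guesses may reflect the observed outcome.
4. Reconcile the synopsis, 10.2.2, 10.2.3 and Appendix 1 with 16.4.2: state what assessors are blinded to, and describe the primary outcome as assessor-blinded only where feasible, with self-rating by participants who are not blinded.
5. Reconcile 13.5 and 13.6.2 with that statement by saying what treatment information the relatedness rater has. Do not move the rating to unblinded site investigators. An SAE rating can fall before the week-26 visit, so question order alone does not settle this item.

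The cost is a change of wording and form order plus one short blinding question at week 26. The ABIC log already exists. The changes will not stop participants from mentioning their coordinator, nor rural assessors from knowing the local phase, and the revised blinding statement should say so.
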